## **Secondary Endpoint #5**

Endpoint Description: Total number of non-elective all-cause hospitalizations

Response Variable Definition: The hospitalizations will be reviewed and adjudicated by a CEC as non-elective all-cause hospitalizations.

Additional Covariates: Age, sex, baseline DLCO, baseline FVC, use of NAC at enrollment, use of standard of care medications at enrollment, and choice of antimicrobial agent prior to randomization.

Handling of Dropouts and Missing Data: All patients will have some information regarding mortality and last visit of follow-up. Lung transplantation will be additional censoring variable in this analyses. The censoring mechanism is assumed to be non-informative. Supportive analyses will be performed to assess the impact of a potential informative censoring.

Diagnostic tests: The additional continuous covariates to be used in the primary analysis model will be assessed for major departures from linearity by inspection scatter plots with LOESS curves. If a departure is observed then a suitable transformation will be explored. The validity of this model in terms of meeting

modeling assumptions will be assessed via standard modeling diagnostics and goodness-of-fit measures.

Statistical Tests: The Poisson regression model will be used to estimate outcome ratio between the two treatment arms: “Standard care + oral antimicrobial therapy” and “Standard care”. The outcome is the total number of non-elective all-cause hospitalizations with model terms for treatment arm, baseline measurement, and covariates. Rates and 95% confidence intervals will summarize the differences between treatment arms.

Interpretation of Results: For Poisson regression models a ratio below 1.00 will indicate a reduction in events for “Standard care + oral antimicrobial therapy” arm. A ratio above 1.00 will indicate increase in events for “Standard care + oral antimicrobial therapy” arm.

## **Secondary Endpoint #6**

Endpoint Description: Change in FVC (L) from randomization to 12 months

Response Variable Definition: The FVC data will be collected at baseline and 12 months. The change from baseline will be calculated for the 12 month values by subtracting the baseline result.

Additional Covariates: Age, sex, baseline DLCO, baseline FVC, use of NAC at enrollment, use of standard of care medications at enrollment, and choice of antimicrobial agent prior to randomization.

Handling of Dropouts and Missing Data: All patients will have some information regarding mortality and last visit of follow-up. Lung transplantation will be additional censoring variable in this analyses. The censoring mechanism is assumed to be non-informative. Supportive analyses will be performed to assess the impact of a potential informative censoring.

Diagnostic tests: The additional continuous covariates to be used in the primary analysis model will be assessed for major departures from linearity by inspection scatter plots with LOESS curves. If a departure is observed then a suitable transformation will be explored. The validity of this model in terms of meeting modeling assumptions will be assessed via standard modeling diagnostics and goodness-of-fit measures.

Statistical Tests: The linear regression model will be used to estimate outcome differences between the two treatment arms: “Standard care + oral antimicrobial therapy” and “Standard care”. The outcome is the measured result at 12 months with model terms for treatment arm, baseline measurement, and covariates. Descriptive statistics will be calculated at baseline and 12 months by treatment group.

Interpretation of Results: For linear models a difference below 0.00 will indicate a reduction in score for “Standard care + oral antimicrobial therapy” arm. A difference above 0.00 will indicate increase in score for “Standard care + oral antimicrobial therapy” arm.

## **Secondary Endpoint #7**

Endpoint Description: Change in DLCO from randomization to 12 months

Response Variable Definition: The DLCO data will be collected at baseline and 12 months. The change from baseline will be calculated for the 12 month values by subtracting the baseline result.

Additional Covariates: Age, sex, baseline DLCO, baseline FVC, use of NAC at enrollment, use of standard of care medications at enrollment, and choice of antimicrobial agent prior to randomization.

Handling of Dropouts and Missing Data:

All patients will have some information regarding mortality and last visit of follow-up. Lung transplantation will be additional censoring variable in this analyses. The censoring mechanism is assumed to be non-informative. Supportive analyses will be performed to assess the impact of a potential informative censoring.

Diagnostic tests: The additional continuous covariates to be used in the primary analysis model will be assessed for major departures from linearity by inspection scatter plots with LOESS curves. If a departure is observed then a suitable transformation will be explored. The validity of this model in terms of meeting modeling assumptions will be assessed via standard modeling diagnostics and goodness-of-fit measures.

Statistical Tests: The linear regression model will be used to estimate outcome differences between the two treatment arms: “Standard care + oral antimicrobial therapy” and “Standard care”. The outcome is the measured result at 12 months with model terms for treatment arm, baseline measurement, and covariates. Descriptive statistics will be calculated at baseline and 12 months by treatment group.

Interpretation of Results: For linear models a difference below 0.00 will indicate a reduction in score for “Standard care + oral antimicrobial therapy” arm. A difference above 0.00 will indicate increase in score for “Standard care + oral antimicrobial therapy” arm.

## **Secondary Endpoint #8**

Endpoint Description: Total number of respiratory infections

Response Variable Definition: all lower respiratory tract infection(s) treated with antibiotic treatment will be collected in follow-up.

Additional Covariates: Age, sex, baseline DLCO, baseline FVC, use of NAC at enrollment, use of standard of care medications at enrollment, and choice of antimicrobial agent prior to randomization.

Handling of Dropouts and Missing Data: The censoring mechanism is assumed to be non-informative. Supportive analyses will be performed to assess the impact of a potential informative censoring.

Diagnostic tests: The additional continuous covariates to be used in the primary analysis model will be assessed for major departures from linearity by inspection scatter plots with LOESS curves. If a departure is observed then a suitable transformation will be explored. The validity of this model in terms of meeting modeling assumptions will be assessed via standard modeling diagnostics and goodness-of-fit measures.

Statistical Tests: A Poisson regression model will be used to estimate outcome ratio between the two treatment arms: “Standard care + oral antimicrobial therapy” and “Standard care”. The outcome is the total number of respiratory infections with model terms for treatment arm, baseline measurement, and covariates. Rates and 95% confidence intervals will summarize the differences between treatment arms.

Interpretation of Results: For Poisson regression models a ratio below 1.00 will indicate a reduction in events for “Standard care + oral antimicrobial therapy” arm. A ratio above 1.00 will indicate increase in events for “Standard care + oral antimicrobial therapy” arm.

## **Secondary Endpoint #9**

Endpoint Description: Change in UCSD-Shortness of Breath Questionnaire from randomization to 12 months

Response Variable Definition: The UCSD-Shortness of Breath Questionnaire data will be collected at baseline and 12 months. For the collect questionnaire data the UCSD-Shortness of Breath score will be calculated. The change from baseline will be calculated for the 12 month values by subtracting the baseline result.

Additional Covariates: Age, sex, baseline DLCO, baseline FVC, use of NAC at enrollment, use of standard of care medications at enrollment, and choice of antimicrobial agent prior to randomization.

Handling of Dropouts and Missing Data:

The censoring mechanism is assumed to be non-informative. Supportive analyses will be performed to assess the impact of a potential informative censoring.

Diagnostic tests: The additional continuous covariates to be used in the primary analysis model will be assessed for major departures from linearity by inspection scatter plots with LOESS curves. If a departure is observed then a suitable transformation will be explored. The validity of this model in terms of meeting modeling assumptions will be assessed via standard modeling diagnostics and goodness-of-fit measures.

Statistical Tests: The linear regression model will be used to estimate outcome differences between the two treatment arms: “Standard care + oral antimicrobial

therapy” and “Standard care”. The outcome is the measured result at 12 months with model terms for treatment arm, baseline measurement, and covariates. Descriptive statistics will be calculated at baseline and 12 months by treatment group.

Interpretation of Results: For linear models a difference below 0.00 will indicate a reduction in score for “Standard care + oral antimicrobial therapy” arm. A difference above 0.00 will indicate increase in score for “Standard care + oral antimicrobial therapy” arm.

### **Secondary Endpoint #10**

Endpoint Description: Change in Fatigue Severity Scale score from randomization to 12 months

Response Variable Definition: The Fatigue Severity Scale Questionnaire data will be collected at baseline and 12 months. For the collect questionnaire data the Fatigue Severity Scale score will be calculated. The change from baseline will be calculated for the 12 month values by subtracting the baseline result.

Additional Covariates: Age, sex, baseline DLCO, baseline FVC, use of NAC at enrollment, use of standard of care medications at enrollment, and choice of antimicrobial agent prior to randomization.

Handling of Dropouts and Missing Data: The censoring mechanism is assumed to be non-informative. Supportive analyses will be performed to assess the impact of a potential informative censoring.

Diagnostic tests: The additional continuous covariates to be used in the primary analysis model will be assessed for major departures from linearity by inspection scatter plots with LOESS curves. If a departure is observed then a suitable transformation will be explored. The validity of this model in terms of meeting modeling assumptions will be assessed via standard modeling diagnostics and goodness-of-fit measures.

Statistical Tests: The linear regression model will be used to estimate outcome differences between the two treatment arms: “Standard care + oral antimicrobial therapy” and “Standard care”. The outcome is the measured result at 12 months with model terms for treatment arm, baseline measurement, and covariates. Descriptive statistics will be calculated at baseline and 12 months by treatment group.

Interpretation of Results: For linear models a difference below 0.00 will indicate a reduction in score for “Standard care + oral antimicrobial therapy” arm. A difference above 0.00 will indicate increase in score for “Standard care + oral antimicrobial therapy” arm.

### **Secondary Endpoint #11**

Endpoint Description: Change in Leicester Cough Questionnaire score from randomization to 12 months

Response Variable Definition: The Leicester Cough Questionnaire data will be collected at baseline and 12 months. For the collect questionnaire data the Leicester Cough Questionnaire score will be calculated. The change from baseline will be calculated for the 12 month values by subtracting the baseline result.

Additional Covariates: Age, sex, baseline DLCO, baseline FVC, use of NAC at enrollment, use of standard of care medications at enrollment, and choice of antimicrobial agent prior to randomization.

Handling of Dropouts and Missing Data:

The censoring mechanism is assumed to be non-informative. Supportive analyses will be performed to assess the impact of a potential informative censoring.

Diagnostic tests: The additional continuous covariates to be used in the primary analysis model will be assessed for major departures from linearity by inspection scatter plots with LOESS curves. If a departure is observed then a suitable transformation will be explored. The validity of this model in terms of meeting modeling assumptions will be assessed via standard modeling diagnostics and goodness-of-fit measures.

Statistical Tests: The linear regression model will be used to estimate outcome differences between the two treatment arms: “Standard care + oral antimicrobial therapy” and “Standard care”. The outcome is the measured result at 12 months with model terms for treatment arm, baseline measurement, and covariates. Descriptive statistics will be calculated at baseline and 12 months by treatment group.

Interpretation of Results: For linear models a difference below 0.00 will indicate a reduction in score for “Standard care + oral antimicrobial therapy” arm. A difference above 0.00 will indicate increase in score for “Standard care + oral antimicrobial therapy” arm.

## **Secondary Endpoint #12**

Endpoint Description: Change in EQ-5D score and SF-12 score from randomization to 12 months

Response Variable Definition: The SF-12 questionnaire data will be collected at baseline and 12 months. The EQ-5D questionnaire data will be collected at baseline and 12 months. For the collect questionnaire data the EQ-5D score and SF-12 score will be calculated. The change from baseline will be calculated for the 12 month values by subtracting the baseline result.

Additional Covariates: Age, sex, baseline DLCO, baseline FVC, use of NAC at enrollment, use of standard of care medications at enrollment, and choice of antimicrobial agent prior to randomization.

Handling of Dropouts and Missing Data:

The censoring mechanism is assumed to be non-informative. Supportive analyses will be performed to assess the impact of a potential informative censoring.

Diagnostic tests: The additional continuous covariates to be used in the primary analysis model will be assessed for major departures from linearity by inspection scatter plots with LOESS curves. If a departure is observed then a suitable transformation will be explored. The validity of this model in terms of meeting modeling assumptions will be assessed via standard modeling diagnostics and goodness-of-fit measures.

Statistical Tests: The linear regression model will be used to estimate outcome differences between the two treatment arms: “Standard care + oral antimicrobial therapy” and “Standard care”. The outcome is the measured result at 12 months with model terms for treatment arm, baseline measurement, and covariates. Descriptive statistics will be calculated at baseline and 12 months by treatment group.

Interpretation of Results: For linear models a difference below 0.00 will indicate a reduction in score for “Standard care + oral antimicrobial therapy” arm. A difference above 0.00 will indicate increase in score for “Standard care + oral antimicrobial therapy” arm.

### **Secondary Endpoint #13**

Endpoint Description: Change in ICEpop CAPability measure for Older people (ICECAP-O) score from randomization to 12 months

Response Variable Definition: The ICECAP-O questionnaire data will be collected at baseline and 12 months. For the collect questionnaire data the ICECAP-O score will be calculated. The change from baseline will be calculated for the 12 month values by subtracting the baseline result.

Additional Covariates: Age, sex, baseline DLCO, baseline FVC, use of NAC at enrollment, use of standard of care medications at enrollment, and choice of antimicrobial agent prior to randomization.

Handling of Dropouts and Missing Data: The censoring mechanism is assumed to be non-informative. Supportive analyses will be performed to assess the impact of a potential informative censoring.

Diagnostic tests: The additional continuous covariates to be used in the primary analysis model will be assessed for major departures from linearity by inspection scatter plots with LOESS curves. If a departure is observed then a suitable transformation will be explored. The validity of this model in terms of meeting modeling assumptions will be assessed via standard modeling diagnostics and goodness-of-fit measures.

Statistical Tests: The linear regression model will be used to estimate outcome differences between the two treatment arms: “Standard care + oral antimicrobial therapy” and “Standard care”. The outcome is the measured result at 12 months with model terms for treatment arm, baseline measurement, and covariates. Descriptive statistics will be calculated at baseline and 12 months by treatment group.

Interpretation of Results: For linear models a difference below 0.00 will indicate a reduction in score for “Standard care + oral antimicrobial therapy” arm. A difference above 0.00 will indicate increase in score for “Standard care + oral antimicrobial therapy” arm.

## IX. Safety endpoints

---

### **Serious adverse events**

Endpoint Description: Frequency and types of serious adverse events (SAEs) during the following-up period of the trial.

Response Variable Definition: SAEs will be identified by the site PI and coded into the MEDRA medical dictionary.

Statistical Tests: The number of patients with one or more SAEs will be tabulated along with the total number of distinct SAEs. Comparison of the “Standard care + oral antimicrobial therapy” and “Standard care” arms will be done with a chi-square test, i.e. the number of patient with one or more events. Other groupings of SAEs maybe generated as deemed necessary.

Interpretation of Results: For cases where “Standard care + oral antimicrobial therapy” rate is less than “Standard care” rate will indicate a reduction for “Standard care + oral antimicrobial therapy” arm. For cases where “Standard care + oral antimicrobial therapy” rate is greater than “Standard care” rate will indicate an increase for “Standard care + oral antimicrobial therapy” arm.

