9. OUTCOME DETERMINATIONS

9.1 Primary Endpoint

The primary endpoint of this study will be the time to first non-elective, respiratory hospitalization or all-cause mortality.

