10.5 Serious Adverse Events

Any adverse Event that meets any of the following criteria: (1) results in death; (2) is life-threatening (i.e. places a participant at immediate risk of death from the event as it occurred); (3) requires inpatient hospitalization or prolongation of existing hospitalization; (4) results in a persistent or significant disability/incapacity; (5) results in a congenital anomaly/birth defect; OR (6) any other adverse event that, based upon appropriate medical judgment, may jeopardize the participant's health and may require medical or surgical intervention to prevent one of the other outcomes listed in this definition (e.g. allergic bronchospasm requiring intensive treatment in the emergency room or at home).

Information about all serious adverse events, whether volunteered by the subject, discovered by investigator questioning, or detected through physical examination, laboratory test or other means, will be collected and recorded on the Serious Adverse Event eCRF.

For this study, all SAEs occurring from the time of drug administration to 30 days post-study completion visit will be captured on the SAE eCRF. As the Month 36 Visit is a Phone Call Visit, review of subjects' medical records is required, in order to evaluate any SAEs within 30 days post-study completion visit. Unless exempted as described below, all SAEs, whether or not deemed drug-related, must be reported by the investigator or qualified designee within 1

business day of first becoming aware of the event. The investigator/qualified designee will enter the required information regarding the SAE into the appropriate module of the IBM Clinical Development, which will automatically result in distribution of the information to the Duke Clinical Research Institute Medical Monitor and Clinical Operations team, and the Network Management Core (NEMO). If IBM Clinical Development is temporarily unavailable, the event, including the investigator-determined causality to study drug, should be reported via a paper back-up SAE form to the DCRI Medical Monitor and Clinical Operations team, and the NEMO. Upon return of the availability of EDC system, the SAE information must be entered into the eCRF.

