13.2 Statistical Monitoring Plan

Safety and efficacy data will be periodically assessed by the DSMB. Safety and efficacy data will be periodically assessed by the DSMB. For ethical reasons, an interim examination of key safety and endpoint data will be performed at regular intervals during the course of the trial. The interim monitoring will also involve a review of the control arm event rates, patient recruitment, compliance with the study protocol, status of data collection, and other factors that reflect the overall progress and integrity of the study. An NHLBI-appointed DSMB will carefully and confidentially review the results of the interim analyses and status reports. If protocol modifications are warranted, close consultation among the DSMB, the NHLBI staff, and the study leadership will be required. A separate DSMB charter outlining the operating guidelines for the committee and the protocol for evaluation of data will be created prior to study enrollment and agreed upon during the initial meeting of the DSMB.

It is anticipated that the DSMB will meet at 6-month intervals to review the accumulating data. The DCRI will create regular reports to track patient enrollment reports, rates of compliance with the assigned testing strategy, and frequency of protocol violations. Prior to each meeting, the data coordinating center will conduct any requested statistical analyses and prepare a summary report along with the following information: patient enrollment reports, rates of compliance with the assigned testing strategy, frequency of protocol violations, and description of SAEs (statistical comparisons of the randomized arms with respect to these SAEs will use chi-square or other appropriate 2-sample methods).

There will be one planned interim review for efficacy. The efficacy review will focus on the composite endpoint of respiratory hospitalization or all-cause death and should occur once 300 enrolled subjects have been followed for 12 months. The Lan-DeMets alpha spending function with O'Brien-Fleming type boundaries will be used for the interim analysis.

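### Primary-endpoint events also count as SAEs, and the SAP's one overall SAE comparison has no companion row without them

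*SAP*

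**What the plan says.** Protocol 10.5 defines an SAE as "Any adverse Event that meets any of the following criteria: (1) results in death", or, among other criteria, "requires inpatient hospitalization or prolongation of existing hospitalization". Protocol 9.1 sets the primary endpoint as "time to first non-elective, respiratory hospitalization or all-cause mortality".

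Protocol 10.5 also says: "Unless exempted as described below, all SAEs, whether or not deemed drug-related, must be reported by the investigator". No exemption is described in the text that follows. The phrase concerns expedited reporting; the same section sends all SAEs to the SAE eCRF.

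The SAP section on serious adverse events (IX) says: "The number of patients with one or more SAEs will be tabulated along with the total number of distinct SAEs". The arms are compared by chi-square on the number of patients with one or more events, and a lower antimicrobial rate is to be described as a reduction for that arm. Other groupings are optional and none is named. Mock Table 5.1 has an overall row, then rows by body system and event name, each with a p-value.

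For the DSMB, Protocol 13.2 says "statistical comparisons of the randomized arms with respect to these SAEs will use chi-square or other appropriate 2-sample methods".

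**The concern.** A non-elective respiratory hospitalization or a death meets the SAE definition, so each one enters the any-SAE row. The row then carries two things at once: toxicity of the antimicrobials and the treatment effect on the primary endpoint. If the strategy works as designed, fewer respiratory hospitalizations can offset extra toxic SAEs. If it makes the disease outcome worse, the excess appears in the primary analysis and again in the SAE comparison. In both cases a reader who wants to know about toxicity apart from the primary outcome has no pooled comparison to look at.

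**Working it through.** **Inputs from the documents.** 500 patients randomized 1:1, so 250 per arm. Table 1 gives 12-month standard-care event rates of 24%, 30% and 36% with reductions of 30% to 35%. Two-sided 0.05 (Protocol 11.3; SAP IV).

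**Assumed, because the documents give no figure.** A baseline toxic-SAE risk q on standard care, doubled to 2q on antimicrobial therapy; other background SAEs of 0%, 10% or 20%, equal in both arms; independence between SAE types; 12-month rates.

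**The plan's own figure first.** Table 1, 30% vs 21%: hazard ratio = ln(0.79)/ln(0.70) = 0.661. With exponential times, uniform 30-month accrual, 12 to 42 months of follow-up and 2% yearly dropout, about 230 events are expected. Power is 87.2% (Freedman) or 88.1% (Schoenfeld), against 87% stated. The other eight rows agree to within 2 points. The design effects used below are therefore the plan's own.

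**Any-SAE rate.** P(any SAE) = 1 − (1 − primary)(1 − background)(1 − toxic). With q = 5%, 30% vs 21% primary events and no background:
- standard care: 1 − 0.70 × 0.95 = 33.5%
- antimicrobial: 1 − 0.79 × 0.90 = 28.9%

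In counts this is about 84 vs 72 of 250, chi-square p = 0.25. The chance of a significant result in the harm direction is about 0.1%.

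**With primary-endpoint events removed.**

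| Background SAEs | Any SAE, standard care vs antimicrobial | Chance of harm signal | Endpoint events removed | Power |
|---|---|---|---|---|
| 0% | 33.5% vs 28.9% | 0.1% | 5.0% vs 10.0% | 57% |
| 10% | 40.2% vs 36.0% | 0.2% | 14.5% vs 19.0% | 27% |
| 20% | 46.8% vs 43.1% | 0.3% | 24.0% vs 28.0% | 17% |

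**Where the reversal stops.** Let c and t be the primary-event rates on standard care and antimicrobial therapy. The any-SAE rates are equal when (1 − c)(1 − q) = (1 − t)(1 − 2q), so q = (c − t)/[2(1 − t) − (1 − c)]. Equal background does not move this point.
- 24% vs 16.8%: 0.072/(1.664 − 0.760) = 8.0%
- 30% vs 21%: 0.090/(1.580 − 0.700) = 10.2%
- 36% vs 25.2%: 0.108/(1.496 − 0.640) = 12.6%
- largest in Table 1, 36% vs 23.4%: 0.126/(1.532 − 0.640) = 14.1%

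Above break-even the row shows an increase: at 24% vs 16.8% with q = 10% it reads 31.6% vs 33.4%.

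**No efficacy benefit.** With 30% in both arms and q = 5% the row reads 33.5% vs 37.0%. The direction is right but diluted, with 13% power.

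**The opposite case (assumed).** Toxicity is 5% in both arms and the primary endpoint worsens from 30% to 40%. The row reads 1 − 0.70 × 0.95 = 33.5% vs 1 − 0.60 × 0.95 = 43.0%, with about a 59% chance of a significant SAE excess that repeats the primary result.

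**The case against.** The strongest reply is that the any-SAE comparison is sound. In a randomized trial, excess deaths or hospitalizations on the assigned strategy are harm, and total serious-event burden is worth reporting. This stands. A reader might go further and infer that the row says nothing about harm from the drug; the documents do not support that.

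Second, a reader might infer that a doubling of toxicity would be hidden from the safety report. It would not be. Table 5.1 tests each body system and event name, the SAP analyses deaths and hospitalizations separately, and investigators assess relatedness. The gap is narrower. These rows spread toxicity over small cells, none of them pools the non-endpoint SAEs, and the SAP addendum lets some SAEs stay uncoded.

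Third, the numbers rest on toxicity rates that the documents do not give, on the full design benefit, and on 12-month rates although SAE collection runs longer. This also stands, so the result is an illustration with a range. The SAP's reduction wording is a directional label, used identically for concomitant medication; it claims nothing about toxicity.

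Finally, the termination letter reports trends toward higher rates of the primary outcome, mortality and SAEs on the intervention, so masking is not what the DSMB saw. Nor can a reader conclude that the SAE trend was merely the primary outcome repeated: the letter gives no counts. The planned row could not separate the two.

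**Conclusion.** The point holds in a limited form. By the protocol's definition, primary-endpoint events are SAEs, and the only overall between-arm SAE comparison the SAP specifies has no counterpart without them. Under Table 1's 30% reduction, a doubling of toxic SAEs would appear as a lower any-SAE rate if the baseline toxic-SAE risk is below about 8%, 10% or 13% (event rates 24%, 30%, 36%), and up to about 14% across all Table 1 scenarios. Above those values, or without the efficacy benefit, the row shows an increase, though a diluted one. At 5% to 10% toxicity and 30% vs 21% events, the false reduction is one of direction and not significant. These figures assume independence, 250 per arm and 12-month rates. A pooled non-endpoint row restores the direction, but at 57% power at best in this illustration, and 27% or 17% with background SAEs, it does not guarantee detection. The change is worth considering; the safety analysis is not invalid without it.

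**What to change.** In SAP IX, mock Table 5.1 and the DSMB SAE report, keep the all-SAE row. Add one supplementary between-arm comparison of patients with at least one SAE that is not itself a primary-endpoint event, meaning a non-elective respiratory hospitalization (as adjudicated, or as site-reported where the addendum's fallback applies) or a death. Continue to report deaths separately by arm. State that the two rows are read together, and that a lower all-SAE rate is not by itself evidence of less drug toxicity.

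Separately, reconcile the exemption phrase in Protocol 10.5 with the text after it, which describes no exemption. This is a drafting matter and does not affect the calculation.

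The cost is some wording and one table row, from SAE, hospitalization and death data that the trial already collects. The downside is that a drug reaction presenting as a respiratory hospitalization or a death drops out of the new row. For that reason the all-SAE row stays and the new row should not carry the safety conclusion alone.
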